### [name] mask design subtypes for filtration testing, fit-testing, and subjective questionnaire (breathability and comfort)

#### **PART ONE - FILTRATION**

*\*Note: all masks that are washed will be washed with gentle soap, specifically All Free & Clear with Oxi. No liquid fabric softener will be used. No fabric softener.*

- 1) Double layer E-100, adult, after washing in machine 50 times, normal dryer temp until dry
  - a. Sanitize cycle
    - i. Ambient air
  - b. If decreased filtration from baseline, will try Cold water, delicate cycle, air dry
    - i. Ambient air
- 2) Single layer E-100 plus cotton print, adult, after washing in machine 50 times, normal dryer temp
  - a. Sanitize cycle
    - i. Ambient air
  - b. If decreased filtration from baseline, will try Cold water, delicate cycle, air dry
    - i. Ambient air
- 3) Double layer cotton mask washed 10x
- 4) Blue surgical mask available online and in stores, unused
- 5) Purple surgical mask provided by MCHS-Mankato to employees and patients, unused
- 6) KN95 available in stores and online, unused
- 7) NIOSH-approved 3M N95, unused

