My mask design (and design subtypes) will be formally tested to determine both their filtration ability as well as their ability to reduce air leak around the mask. Filtration will be tested using a particle counter that detects particles down to 0.3 microns. Specifically, we will be using the Grainger 23V750 particle counter. Ambient air testing will be completed to determine baseline comparison [2]. At least 8 measurements of each subtype will be performed to assure statistical significance [2]. Filtration will be tested against ambient air as well as in front of forced air from a stationary fan. Air speed will be measured with an anemometer and compared to average speeds reported for coughing and forced exhalation: human ventilation at rest is about 6 LPM, while increased several fold with activity [21, 37]. Of note, we will also test subtypes with one layer of E-100 fabric with an overlying decorative cotton layer, as the general public appears more compliant with personalized mask styles, and therefore would potentially prefer this alternative when comparing style versus function.

To determine the best method for washing/decontamination, we will test masks prior to washing as well as at various settings on a standard washing machine (see specific subtypes below). This data will then be compared to that of our standard medical grade N95 mask as well as to standard hospital grade surgical masks. I will also compare it to the more common non-medical masks currently being produced for the general population. We will determine breathability and comfort via a questionnaire given to a group of voluntary health care workers.

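### Does the wash-setting rule in Part One lack a baseline because the list has no unwashed E-100 mask?

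*Protocol*

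**What the plan says.** Two places in the Protocol bear on this.

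The narrative under RESEARCH IDEA/PRIMARY STUDY AIM states the purpose, "To determine the best method for washing/decontamination", and then how it will be met: "we will test masks prior to washing as well as at various settings on a standard washing machine (see specific subtypes below". The same section sets the replication, "At least 8 measurements of each subtype will be performed to assure statistical significance [2", and uses the word baseline once, for something else: "Ambient air testing will be completed to determine baseline comparison [2". It also announces two air conditions: "Filtration will be tested against ambient air as well as in front of forced air from a stationary fan".

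The list under PART ONE - FILTRATION has two E-100 items. Item 1 is "Double layer E-100, adult, after washing in machine 50 times, normal dryer temp until dry" and item 2 is "Single layer E-100 plus cotton print, adult, after washing in machine 50 times, normal dryer temp". Each has (a) a sanitize cycle and (b) a conditional step worded "If decreased filtration from baseline, will try Cold water, delicate cycle, air dry". Item 3 is a cotton mask after 10 washes. Items 4 to 7 are comparator masks, each marked as unused.

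**The concern.** The list states wash status with some care. It says how often the E-100 and cotton masks were washed and which comparators are unused, yet no E-100 mask appears in an unwashed state. Steps 1b and 2b nevertheless depend on a fall from baseline. If the list were the complete schedule of measurements, there would be no reading to compare against.

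The comparison matters because it decides whether one wash setting or two are tested for each subtype, and finding the best way to wash the mask is a stated purpose. The narrative also asserts that the fabric keeps its effectiveness through repeated washing, and only a before-and-after comparison can check that for filtration. There is a timing risk as well: once a mask has been washed, its own unwashed reading is lost.

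The narrative's one use of the word baseline concerns ambient air, which could send a reader to the wrong reference. The forced-air test raises a similar doubt, since the narrative promises it and the list names only ambient air.

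**Working it through.** The Protocol gives no standard deviation, effect size or power for filtration, so the check is a count and a comparison of passages.

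1. **Count of the list.** E-100 conditions are 1a, 1b, 2a and 2b, which makes 4. Both parent items are headed as after 50 washes, so unwashed conditions number 0 of 4. The factual part of the concern is correct.

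2. **Candidates for the baseline.**
   - *Ambient air without a mask.* Taking filtration in the usual way as 1 − (count behind the mask ÷ ambient count), no mask gives 1 − 1 = 0. Apart from measurement noise, a mask cannot fall below 0, so a decrease from this reference has no meaning. Ambient air supplies the denominator.
   - *The 93–96% figure in the narrative.* It is described as unofficial, refers to the material, and gives neither wash state nor number of layers. It cannot be the reference for a single E-100 layer under cotton.
   - *The pre-wash test in the narrative.* It is measured in the same study and on the same outcome, and it precedes washing. It fits the wording of 1b and 2b.

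   One of three candidates works.

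3. **Is the list complete in itself?** Its heading calls it a list of mask design subtypes. It names no particle counter and no number of readings. It names an air condition under items 1 and 2 only, and none under items 3 to 7. The counter, the minimum of 8 readings and the comparison plan are all in the narrative. The list therefore cannot be carried out without the narrative, and the narrative contains the pre-wash test.

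4. **What naming the baseline would add.** Two unwashed E-100 conditions at the minimum of 8 readings make 2 × 8 = 16 readings. These follow from the narrative's own promise and its own minimum, so against the whole protocol they are not new.

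5. **Is the reading lost if it is missed at first?** Only the pairing within a mask would be lost. A fresh unwashed mask of the same construction can be read at any time. The narrative puts materials below $1.50 per mask. Even with a separate mask for each reading, that is below 16 × 1.50 = $24, assuming the price holds for both constructions.

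**The case for a change.** The strongest reply is that a bench team works from the itemised list, and a list that marks some masks as unused seems to say by omission that the E-100 masks are tested only when washed. An analysis plan cannot later supply readings that nobody took. The pointer in the narrative to the subtypes below also suggests that the list should show everything the sentence promises.

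Part of this stands. The list would be clearer with the unwashed state written in, and the reader does have to infer what baseline means. But a team using the list alone would also not know which counter to use or how many readings to take, so that team is not a realistic one. The pointer directly follows the words on washing-machine settings and can refer to those alone. A reading taken before washing is a time point for a subtype already listed, which explains why it has no line of its own.

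A second reply is that even a named baseline leaves the size of decrease open. That is true. If washing has no effect and any lower mean counts, with symmetric, continuous measurement error, the step would be triggered with probability 0.5 per subtype. For at least one of two independent subtypes the probability is 1 − 0.5² = 0.75. The consequence of a false trigger is that the gentler setting is also tested, at 8 further readings per subtype. This adds information on the stated purpose and biases no comparison. It is also a matter that a statistical analysis plan can settle.

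The forced-air mismatch is of the same kind. The narrative commits to it and the list is abbreviated. It has no bearing on the baseline.

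**Conclusion.** The observation is accurate but no change to the plan follows. None of the 4 listed E-100 conditions is unwashed, and 1b and 2b do not say what baseline means. Read as a whole, the Protocol promises the pre-wash test and leaves it as the only usable reference, so both subtypes have a baseline and the conditional step can be carried out. The claims that the second setting is undetermined and that the effect of washing cannot be estimated hold only if the narrative is ignored.

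This rests on two assumptions: that the team follows the narrative together with the list, and that the promise to test masks before washing covers both E-100 constructions, as its general wording indicates. The residue is a labelling slip in a bench sub-step. It does not alter the comparisons of washed E-100 with other masks, the fit test or the survey.

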#### **PART TWO – FIT TESTING/AIR LEAK**

Ideal demographics for voluntary subjects:

- 1) Health care worker having passed N95 fit test within the past year
- 2) No recent history of hypertension, pneumonia, or uncontrolled asthma

## IRB Protocol – Supplement

[name] FAAP, Instructor of Pediatrics and Adolescent Medicine

20 December 2020

Page | 6

- 3) No facial hair, specifically no beard
- 4) No respiratory illness within the 2 weeks prior to testing
- 5) Not pregnant
- 6) Both genders
- 7) Wide range of ages 18+
- 8) Wide representation of race/ethnicity
- 9) Spectrum of occupations (i.e. physician, RN, RT, etc)
- 10) Wide range of BMI (will ask for height and weight to calculate BMI)

### **Qualitative fit testing: [39]**

Will perform exact procedure used at MCHS-Mankato for annual N95 fit testing for HCW personnel.

For each subject:

- 1) Don N95, perform user seal check, wait 5 minutes.
- 2) Perform fit test with N95 control using Bitrix solution:
  - a. Normal breathing
  - b. Deep breathing
  - c. Turn head side to side
  - d. Turn head up and down
  - e. Talking
  - f. Grimacing
  - g. Bending over
  - h. Normal breathing again
- 3) If fails N95 fit test, still proceed.
  - a. Will allow for collection of data comparing if fit of [name] mask is better than fit with N95.
- 4) Wait at least 5 minutes, and until no taste of Bitrix.
- 5) Don [name] mask (ideally the mask after being washed 50 times on sanitize cycle), perform user seal check, wait 5 minutes.
- 6) Perform fit test with [name] mask using Bitrix solution:
  - a. Normal breathing
  - b. Deep breathing
  - c. Turn head side to side
  - d. Turn head up and down
  - e. Talking
  - f. Grimacing
  - g. Bending over
  - h. Normal breathing again
- 7) Wait at least 5 minutes, and until no taste of Bitrix.
- 8) Perform 2nd fit test with N95 control using Bitrix solution:
  - a. Normal breathing
  - b. Deep breathing
  - c. Turn head side to side
  - d. Turn head up and down
  - e. Talking
  - f. Grimacing

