## IRB Protocol – Supplement

[name] FAAP, Instructor of Pediatrics and Adolescent Medicine

20 December 2020

Page | 7

- g. Bending over
- h. Normal breathing again

9) Wait at least 5 minutes, and until no taste of Bitrix.

10) Perform 3rd fit test with N95 control using Bitrix solution:

- a. Normal breathing
- b. Deep breathing
- c. Turn head side to side
- d. Turn head up and down
- e. Talking
- f. Grimacing
- g. Bending over
- h. Normal breathing again

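### Fit tests run in one fixed order (N95, study mask, N95, N95), so the first N95-versus-study-mask contrast mixes mask with test order; randomise the first two tests.

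*Protocol*

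**What the plan says.** The procedure in the protocol's section on qualitative fit testing (Part Two) is a single numbered list applied to each subject.

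- Steps 1–2: the N95 is put on ("Don N95, perform user seal check, wait 5 minutes") and tested.
- Step 3: "If fails N95 fit test, still proceed". Step 3a gives the reason: "Will allow for collection of data comparing if fit of [name] mask is better than fit with N95".
- Steps 5–6: the study mask is put on ("Don [name] mask (ideally the mask after being washed 50 times on sanitize cycle), perform user seal check, wait 5 minutes") and tested, once.
- Steps 8 and 10: second and third "fit test with N95 control using Bitrix solution". Neither has a donning line, seal check or wait of the kind written in steps 1 and 5.
- Steps 4, 7 and 9, between tests: "Wait at least 5 minutes, and until no taste of Bitrix".

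Two other statements bear on the point. The section opens with "Will perform exact procedure used at MCHS-Mankato for annual N95 fit testing for HCW personnel", and the first item for volunteers in Part Two is "Health care worker having passed N95 fit test within the past year". The protocol mentions no randomisation, counterbalancing or alternative order. It sets a minimum of 40 volunteers and gives no expected pass rate.

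**The concern.** The study mask is always the second test of the session, and the outcome is a pass or fail that depends on whether the volunteer tastes the solution. If alertness, taste sensitivity or handling of the test changes between the first and second test, that change appears as a difference in fit between the masks. Its direction is unknown, so it could flatter the study mask or count against it.

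This is settled when the tests are done. Once all volunteers have been tested in one order, an analysis can separate mask from position only by assuming the shape of the order effect.

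**Working it through.** **1. What each contrast estimates.** Let δ be the true difference in pass rate (study mask minus N95) and a₁ to a₄ the pass rate that an identical mask would have at tests 1 to 4. The study mask is at test 2.

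- Test 2 against test 1: δ + (a₂ − a₁)
- Test 2 against the mean of tests 1 and 3: δ + a₂ − (a₁ + a₃)/2
- Test 2 against the mean of all three N95 tests: δ + a₂ − (a₁ + a₃ + a₄)/3
- First two tests, order balanced: ½[δ + (a₂ − a₁)] + ½[δ + (a₁ − a₂)] = δ

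**2. Bias under two assumed shapes, δ = 0.**

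| Assumed pass rates, tests 1–4 | vs test 1 | vs mean of 1 and 3 | vs mean of 1, 3, 4 | Balanced |
|---|---|---|---|---|
| Linear: 80, 85, 90, 95% | 85 − 80 = +5 | 85 − 85 = 0 | 85 − 88.3 = −3.3 | 0 |
| First-test effect: 90, 95, 95, 95% | 95 − 90 = +5 | 95 − 92.5 = +2.5 | 95 − 93.3 = +1.7 | 0 |

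Figures are percentage points. The use of the repeat N95 tests that removes a linear drift leaves half of a first-test effect. No single choice works for both shapes.

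**3. Chance of a false finding.** The sample size of 40 is from the protocol. Everything else is assumed: identical masks, results independent within a volunteer, and a two-sided exact McNemar test at 0.05 on the first pair. With pass probabilities p₁ and p₂ at tests 1 and 2, a volunteer in the fixed order passes only with the study mask with probability p₂(1 − p₁), and only with the N95 with probability p₁(1 − p₂). For 90% then 95% these are 0.95 × 0.10 = 0.095 and 0.90 × 0.05 = 0.045. Exact enumeration gives:

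| p₁ then p₂ | Fixed: study mask better | Fixed: study mask worse | Balanced 20/20, each direction |
|---|---|---|---|
| 95% then 100% | 1.4% | 0.0% | 0.01% |
| 90% then 95% | 4.4% | 0.03% | 0.5% |
| 85% then 95% | 18.0% | 0.0% | 0.7% |
| 95% then 90% | 0.03% | 4.4% | 0.5% |
| 95% then 85% | 0.0% | 18.0% | 0.7% |

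With no order effect the chance in one direction is 0.2% at a pass rate of 95%, 0.8% at 90% and 1.1% at 85%. A 5-point rise from 90% therefore multiplies the chance of wrongly favouring the study mask by about five (4.4/0.8), although total rejection is still only 4.4%.

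**4. Sensitivity.** With the strongest within-person correlation these rates allow (no discordance in the other direction), the fixed-order chance is 1.4% for 90% then 95% and 20.6% for 85% then 95%. At lower starting pass rates of 60–70% (simulation, independent results), a 10-point rise gives 11–12% total false findings and a 15-point rise 22–27%, against about 3% with no shift. Across all shifts tried, from −10 to +20 points, balanced order gave 1.7–3.2%.

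**The case against.** The order effect is hypothetical: the protocol gives neither its size nor its direction, and it already guards against the most obvious sources. Testing resumes only when no taste remains, and volunteers know the N95 procedure. A high first N95 pass rate is plausible, which caps any upward shift; from 95% the larger errors go against the study mask. A 5-point shift does not push total rejection above 5%, and strong correlation lowers it to 1.4%. The protocol also does not say that test 1 against test 2 is the comparison; the analysis plan may use the N95 tests on both sides. All of this stands, and it limits the likely size. It does not remove the aliasing, because the bracketing tests correct the bias only for an assumed shape of drift.

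The best counter-argument concerns carryover. Testing the N95 first keeps study-mask exposure out of that baseline. Suppose study-mask-first testing lowers the next N95 pass rate from 95% by 10 points. The balanced design is then biased towards the study mask by 10/2 = 5 points and declares it better 4.2% of the time, against 0.2% in the fixed order; a 20-point drop gives 17.5%. Balancing does not cure unequal carryover. But this needs exposure to affect the next test despite the wait until no taste remains, which is there to prevent it.

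The missing donning lines in steps 8 and 10 may be covered by the site's own procedure. They are a drafting gap and not part of the case on order.

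**Conclusion.** The concern holds. Mask and test position are fully aliased in the first N95-versus-study-mask pair, which follows from the written sequence and needs no assumption. The bias equals whatever shift occurs between tests 1 and 2. How often that would mislead depends on assumed rates: with 40 volunteers, 4.4% for a 5-point rise from 90% and 18.0% for a 10-point rise from 85%, against 0.5% and 0.7% in balanced order. The fixed order is not required for screening, since step 3 lets volunteers continue whatever the first N95 result. The change should be made; confidence is medium because the real order effect could be small.

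**What to change.** Randomise volunteers 1:1 to N95 first or study mask first for the first two tests. Base the mask comparison on those two tests and account for order in the paired analysis. Keep the waits in steps 4, 7 and 9 and the two later N95 tests. In steps 8 and 10, state that the N95 is put on again with the same seal check and wait as in step 1.

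The cost is an allocation list, a short change of wording and a slightly more complex paired analysis. Each volunteer still has three N95 tests and one study-mask test. Unequal carryover between the masks would remain a limitation and should be acknowledged.

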## IRB Protocol – Supplement

[name] FAAP, Instructor of Pediatrics and Adolescent Medicine

20 December 2020

Page | 7

- g. Bending over
- h. Normal breathing again

9) Wait at least 5 minutes, and until no taste of Bitrix.

10) Perform 3rd fit test with N95 control using Bitrix solution:

- a. Normal breathing
- b. Deep breathing
- c. Turn head side to side
- d. Turn head up and down
- e. Talking
- f. Grimacing
- g. Bending over
- h. Normal breathing again

### **PART THREE – COMFORT AND BREATHABILITY**

#### Questionnaire components:

- 1) Smoking status
- 2) Height and weight
- 3) Rate comfort on a scale from 1-5
- 4) Rate communicability on a scale from 1-5
- 5) Rate sense of protection on a scale from 1-5
- 6) Rate perceived resistance to breathing on a scale from 1-5
- 7) Determine preferred mask – [name] mask vs N95 vs others

Upon completion of my research, we hope to demonstrate that the [name] mask is a superior alternative in multiple settings, including hospitals in developing countries with little or no N95 mask access, non-hospital settings such as nursing homes (where there has been a significantly higher rate of COVID-19 transmission and death), businesses and schools, churches and other religious settings, as well as for other members of the general population, including those with high risk for COVID-related complications.

